13.2 Statistical Analysis

For continuous variables, descriptive statistics will include the number of subjects (n), mean, standard deviation, median, inter-quartile range, minimum, and maximum, based upon subjects with reported data for the variable being analyzed. Frequencies (numerator and denominator), percentages, and 95% confidence intervals will be displayed for categorical data. Percentages by categories will be based on the number of subjects with no missing (unreported) data for the specific variable being analyzed and the count of the patients for each individual level of the categorical variable (the level specific numerators). Percentages will add up to 100%, unless otherwise indicated.

There are no plans to impute missing data and there are no plans to explicitly report missing data (counts and/or percentages) in the tables for all variables as part of the planned study report content. Variations in the reported sample sizes within and/or between relevant tables can be used to ascertain insights into unreported data. In some cases, unreported data may be due to it not being clinically relevant to a particular patient or may represent expected data that was not collected. Selected analyses pertaining to unreported and/or missing data may be discussed and considered as future findings warrant.

The exploratory nature of the study suggests that the statistical focus will be on estimation and hypothesis generation and not hypothesis testing. Though p-values will be reported as apropos, point estimates, and 95% confidence intervals will be used to guide exploratory analyses for potentially clinically meaningful differences or changes to be discussed and evaluated.

Primary within treatment group analyses of change from baseline will utilize paired tests (e.g. paired t-tests, McNemar chi-square) or similar non-parametric tests as appropriate, to compare the 30-day measurement to baseline.

Secondary between treatment group comparative analyses of change from baseline will utilize ANCOVA or similar methods as appropriate. These methods will include the 30-day measurement as the dependent (response) variable, while the baseline measurement and treatment group will be the independent variables. Assessments of any interactions between the baseline measurement and treatment group will be performed.

Other exploratory comparisons, when performed, will utilize chi-square, ANOVA, t-test, and appropriate non-parametric tests, unless otherwise specified.

In the case of multiple comparisons, when performed, the Hochberg adjustment method (1988) will be used to control the family-wise error rate.

Multivariable models (e.g., linear regression or logistic regression) may be used to assess the predictive relationships and control for possible confounding imbalances of selected multiple variables to specific outcome measures of interest.

Any formal null hypothesis-based statistical comparisons will be made using two sided tests at the $\alpha=0.05$ significance level unless specifically stated otherwise. All null hypotheses will be of no inter-group difference, all alternative hypotheses will be two-sided, unless specifically stated otherwise.

All data processing, summarization, and analyses will be performed using R Version 3.6.0 or higher.

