3.0 Study Objective

The primary objective of the study is to assess the effectiveness of bilateral Flexitouch Plus use with conservative care based upon:

- Circumferential measurements at ankle, mid-calf, lower thigh, upper thigh, hip, and waist,
- Quality of life (RAND 36-Item Health Survey 1.0), and
- Patient-reported symptoms and pain intensity (PROMIS Pain Interference – Short Form 6b, Wong-Baker Faces Scale, and the NIH Toolbox numerical rating scale (NRS)).

Exploratory endpoints include:

- Mobility (PROMIS Mobility v2.0), and
- Bioimpedance measurements (Whole Body and Segmental Extracellular Water/Total Body Water (ECW/TBW) ratios using InBody 770).
- Comparing all objectives and endpoints between treatment groups.

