4.0 Study Design

This is a prospective, randomized, two-arm study comparing Flexitouch Plus with conservative care to conservative care alone (Figure 1). This post-market study involves on label use of the Flexitouch Plus device given eligible patients must have concurrent diagnosis with lymphedema (as noted by Stage 2/3 lipedema with presence of secondary swelling upon physical exam) and obtain the device through normal commercial means (self-pay, patient assistance, or insurance programs).

[figure not shown]

Figure 1. Study Design

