4.1 Endpoint Mapping

Endpoint	Outcome Measure	Analysis
Primary	
 Circumferential Measurements 	
 Calculate percent reduction at Follow-up compared to Baseline for 6 sites on each leg as well as a composite total.
Primary	
 Quality of Life 	
 Compare Follow-up RAND SF36 score to Baseline.¹
Primary	
 Symptoms & Pain Intensity 	
 Compare Follow-up PROMIS Pain Interference², Wong-Baker Faces Scale, and the NIH Toolbox numerical rating scale (NRS) scores to Baseline.
Exploratory	
 Mobility 	
 Compare Follow-up PROMIS Mobility score to Baseline.²

¹ https://www.rand.org/health-care/surveys_tools/mos/36-item-short-form/scoring.html

² http://www.healthmeasures.net/index.php?option=com_instruments&task=Search.pagination&Itemid=992

Endpoint	Outcome Measure	Analysis
Exploratory	
 • Bioimpedance Measurements 	
 • Calculate mean reduction at Follow-up compared to Baseline for the Segmental (Right/Left Arm/Leg, Trunk) and Whole Body Extracellular Water (ECW)/Total Body Water (TBW) ratios.

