13.0 Statistical Methods

13.1 Sample Size Determination

The study is not formally powered for a specific primary hypothesis, thus no formal power/sample size estimation was performed. The study sample size was determined based upon a desire to be able to estimate the means of the primary within group endpoints, using 95% confidence intervals, with the estimation of the endpoint means to have a precision (half width of the confidence intervals) of approximately 40% of the observed standard deviation. To achieve these parameters, we have determined a target analyzable sample size of 15 subjects (30 total legs as the observational units) per group. To accommodate an expected attrition rate of up to 20%, a total of 3 subjects per arm will be replaced, if they fail to fully complete the study.

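### The primary analysis of this 1:1 randomised trial is within-arm change from baseline, so its primary result cannot be attributed to the device

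*Combined protocol and SAP*

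**What the plan says.** Section 4.0 describes a "prospective, randomized, two-arm study comparing Flexitouch Plus with conservative care to conservative care alone", and 4.4 sets the allocation at 1:1. The primary objective in 3.0 is to "assess the effectiveness of bilateral Flexitouch Plus use with conservative care".

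The analysis hierarchy does not follow from that design:

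- **13.2, primary:** "Primary within treatment group analyses of change from baseline will utilize paired tests".
- **13.2, secondary:** "Secondary between treatment group comparative analyses of change from baseline will utilize ANCOVA". Follow-up is the response; baseline and treatment group are the independent variables.
- **3.0:** "Comparing all objectives and endpoints between treatment groups" is a bullet under the exploratory endpoints, so the same comparison has a different rank there.
- **4.1:** every primary endpoint is defined against baseline only, for example "Compare Follow-up RAND SF36 score to Baseline". No contrast between arms is named.
- **13.1:** the sample size was chosen "to be able to estimate the means of the primary within group endpoints".

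The plan is open about its limits. Section 13.1 says that the study is not powered for a specific hypothesis, and 13.2 says that the "statistical focus will be on estimation and hypothesis generation and not hypothesis testing".

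**The concern.** A control group is randomised so that whatever would have happened without the device can be subtracted. The primary analysis does not make that subtraction. Change in the device arm contains at least four components:

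- any effect of the device;
- conservative care, which 2.3.2 leaves uncontrolled and on which 6.10 has patients trained after randomisation;
- time, including regression to the mean;
- response to knowing the allocation. The envelope is opened in front of the subject (6.5), and the quality-of-life, pain and symptom endpoints are self-reported.

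A positive primary result would therefore show that these women changed, not that the device caused the change. Setting the two arms' paired tests side by side does not repair this. With identical true change in both arms, one test can reach significance and the other miss it by chance. As ranked, the control arm contributes nothing to the primary answer on effectiveness.

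**Working it through.** **Inputs from the documents.** 15 analysable women (30 legs) per arm, and a target 95% CI half-width of about 40% of the SD (13.1); two-sided 5% tests (13.2). The documents give no effect size, no expected change in either arm and no baseline to follow-up correlation, so those below are assumptions shown as ranges.

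**1. The plan's own figure.** Half-width in SD units for one arm's mean is t(0.975, n−1)/√n.

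- n = 30 legs taken as independent: 2.045/√30 = 0.373. With 14 df instead: 2.145/√30 = 0.392. Both are close to 0.40.
- n = 15 women: 2.145/√15 = 0.554.

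The stated precision is therefore reproduced only for a within-arm mean with legs treated as independent. It says nothing about the difference between arms.

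**2. What the primary test does when the device does nothing.** Assume zero device effect, the same true change δ (in SDs of the change score) in both arms, 15 women per arm and one value per woman. The probability p that the device-arm paired t-test is significant comes from the non-central t with 14 df and non-centrality δ√15. The arms are independent, so the probability that the device arm is significant and the control arm is not equals p(1−p).

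| Shared change δ | p | p(1−p) |
|---|---|---|
| 0.3 | 0.192 | 0.155 |
| 0.5 | 0.438 | 0.246 |
| 0.8 | 0.821 | 0.147 |

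A simulation of 100,000 trials gave 0.155, 0.248 and 0.147 for the last column. The between-arm t-test was significant in 0.049, 0.049 and 0.051 of the same trials.

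The values of p are not false-positive rates. The paired test correctly rejects its own null of no change. The error lies in attributing that change to the device.

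**3. What the between-arm test does and does not protect against.** It holds at 5% only if all non-device change is shared. If the device arm alone has an extra open-label response of 0.3 or 0.5 SD (assumption), the two-sample t-test with 15 per arm is significant with probability 0.125 or 0.262.

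**4. Between-arm precision at the planned size.**

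- In SDs of the change score: t(0.975, 28)·√(2/15) = 2.048 × 0.365 = 0.748.
- In follow-up SDs (equal SD at both visits, correlation r), unadjusted change score: 0.748·√(2(1−r)) = 0.748 at r = 0.5 and 0.473 at r = 0.8.
- On the same scale, ANCOVA: t(0.975, 27)·√(2/15)·√(1−r²) = 2.052 × 0.365 × √(1−r²) = 0.649 at r = 0.5 and 0.450 at r = 0.8.

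**The case against.** The strongest reply is that the plan promises no causal claim. It calls itself exploratory, has no powered hypothesis, gives its purpose in 2.1 as an association, and already specifies an ANCOVA for the randomised comparison. The same between-arm estimate will be produced whatever its rank, and nowhere does the plan propose to compare the two paired tests. The objective also names the device together with conservative care, so some of the mixing is part of what is being studied.

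The exploratory label and the planned ANCOVA are real, and they make the remedy cheap. They do not change what the primary analysis estimates: a study aimed at estimation still has to estimate the quantity its objective asks for. The wording in 2.1 does not displace effectiveness as the stated primary objective. Reading the objective as the whole regimen still leaves time and open-label response inside the estimate. The end of 13.2 makes all null hypotheses ones of no difference between groups unless stated otherwise, which fits a between-arm primary analysis better than the present one.

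Three cautions stand.

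- The discordance figures describe a likely misreading, not a planned analysis.
- The illustration uses one value per woman, as for the questionnaires. With 30 legs treated as independent, the device-arm figures become 36%, 75% and 99%, and the discordance figures 23%, 19% and 1%.
- The ANCOVA has problems of its own: a 30-day response in 13.2 against follow-up at 4–12 weeks in Table 1, and removal or replacement of randomised women (Table 1, 6.10, 13.1). These are separate points that also affect the current primary analysis.

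**Conclusion.** The concern holds and must be fixed; confidence is high. The hierarchy is consistent across 4.1, 13.1 and 13.2, so this is not a slip of wording, and the randomised comparison carries two different ranks in 3.0 and 13.2. As written, the primary result cannot answer the primary objective.

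That conclusion follows from the design and needs no numerical assumption. The illustrative size does: with no device effect and a shared change of 0.3 to 0.8 SD, a significant device-arm result is expected in 19% to 82% of trials. The between-arm comparison is the right primary quantity, but it is imprecise at 15 per arm and does not remove unequal open-label response. It should be presented as estimation.

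**What to change.** - **3.0, 4.1 and 13.2:** make the baseline-adjusted ANCOVA difference between arms, with its 95% CI, the primary analysis of the primary endpoints, and give that comparison the same status in every section. Report within-arm changes as descriptive.
- **13.2:** use one value per woman, for example the mean of both legs, or a model that accounts for two legs per woman. Keep the baseline-by-treatment interaction as a separate check outside the primary estimate.
- **13.1:** add the between-arm precision at 15 per arm: a half-width of about 0.75 SD of the change score, or about 0.65 to 0.45 follow-up SD with ANCOVA if r is 0.5 to 0.8.
- **Limitations:** state that unequal open-label response on self-reported scales remains possible.
- **Keep** the exploratory, not-powered label and the sample size.

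The cost is wording in four sections and IRB approval of the change (12.1). It should be made before the data are analysed, because re-ranking afterwards would be less credible. No patients or data are added. The downside is a wider and less flattering headline interval: a half-width of 0.75 SD of change between arms, against 0.55 SD for one arm's mean with 15 women.

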Intermittent Pneumatic Compression (IPC) devices are often used as home-therapy to treat secondary lymphedema or lipo-lymphedema (lipedema with swelling) and may be helpful in preventing the progression of lipedema. IPC use moves lymphatic fluid and supports the elimination of proteinaceous fluids, thus leading to improved patient-reported symptoms, decreased limb girth and volume, increased elasticity of tissues, and fewer episodes of infection (1-3). Szolnoky reported daily treatment with CDT, IPC, and multilayered short-stretch bandaging performed for 5 days led to significant improvements in leg volume, capillary fragility, and pain in women with lipedema (4).

The purpose of this study is to assess whether 3-4 weeks of IPC usage is associated with alleviation of symptoms and improvement in quality of life in women with lipo-lymphedema (lipedema with swelling).

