4.2 Subject Selection

The target population includes patients who have bilateral lipedema, meet the criteria listed below, and have provided informed consent.

4.2.1 Inclusion Criteria:

1. Female age 18-70 years.
2. Stage 2-3 (Schmeller Type 2-3) lipedema with secondary lymphedema.
3. Willing and able to follow prescribed care for study period.
4. Able to access (via self-pay, patient assistance, or insurance programs) prescribed care within 60 days of Baseline visit.

4.2.2 Exclusion Criteria:

1. BMI > 50.
2. Heart failure (acute pulmonary edema, decompensated acute heart failure).
3. Pacemaker or implantable cardioverter defibrillator (ICD).
4. Acute venous disease (acute thrombophlebitis, acute deep venous thrombosis, acute pulmonary embolism).
5. Severe peripheral artery disease (critical limb ischemia including ischemic rest pain, arterial wounds, or gangrene).
6. Active skin or limb infection/inflammatory disease (acute cellulitis, other uncontrolled skin or untreated inflammatory skin disease) on the arms or trunk.
7. Active cancer (cancer that is currently under treatment, but not yet in remission).
8. Poorly controlled kidney disease (glomerular filtration rate < 30 mls per minute), hypoproteinemia, pulmonary hypertension, hypothyroidism, cyclic edema, or Munchausen Syndrome.
9. Any circumstance where increased lymphatic or venous return is undesirable.

10. Currently pregnant or trying to become pregnant.

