5.0 Study Assessment

Case Report Forms (CRFs) and Data Clarification Forms (DCFs) will be used for data collection and query handling. The Investigator will ensure the accuracy, completeness, and timeliness of the data recorded.

All data will be entered into an Excel spreadsheet and validated to confirm integrity of data entry. Data may be transferred to an electronic data capture system at some point. When all data have been coded, validated, and signed, the database will be locked (password protected with copy saved as PDF), and available for analysis.

The study schedule of activities is shown in Table 1.

Table 1. Schedule of Activities

Procedures	Baseline (Day 0)	Follow-up (4-12 weeks)
Informed Consent	X	
Demographics & Medical History	X	
Inclusion/Exclusion Assessment	X	
Pregnancy Test (if applicable)	X	
Vitals	X	X
Physical Exam	X	X
Circumferential Measurements	X	X [^]
Bioimpedance Measurements	X	X [^]
QOL Assessment (RAND SF-36)	X	X
Mobility Assessment (PROMIS Mobility)	X	X
Symptom & Pain Intensity Assessment (PROMIS Pain Intensity, NRS Pain & Symptom Scale, Wong-Baker Faces Scale)	X	X
Randomization	X	
Training on Flexitouch Plus and/or Conservative Care*	X	
Adverse Event, Complication, & Device Observation Assessment	X	X

* If subject is unable to obtain prescribed care and complete training on use within 60 days of the Baseline visit (e.g., due to insurance coverage/scheduling delays, etc.), the subject will be considered a screen failure.
 
[^] Optional: Circumferential and bioimpedance measurements may be taken again after an in-clinic treatment with Flexitouch Plus.
		

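### Section 13.2 analyses a 30-day value, but the only Follow-up (4-12 weeks) is not tied to device training, which may finish as late as 60 days after Baseline

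*Combined protocol and SAP*

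**What the plan says.** The documents time the outcome in three ways.

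- **Section 13.2 (analysis).** The primary paired tests are meant "to compare the 30-day measurement to baseline". The between-group ANCOVA uses the same value: "These methods will include the 30-day measurement as the dependent (response) variable".
- **Section 5.0, Table 1 (schedule).** There are two columns, headed "Baseline (Day 0") and "Follow-up (4-12 weeks"). No visit is labelled day 30. Section 4.1 refers to Follow-up for the outcome measures and gives no day.
- **Section 2.1 (purpose).** The study is to "assess whether 3-4 weeks of IPC usage is associated with alleviation of symptoms".

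The start of treatment may come well after Baseline. Section 4.2.1 asks that subjects can access "prescribed care within 60 days of Baseline visit". Table 1 marks "Training on Flexitouch Plus and/or Conservative Care" in the Baseline column, but its footnote makes a subject a screen failure only in this case: "If subject is unable to obtain prescribed care and complete training on use within 60 days of the Baseline visit". Section 6.10 sets the same 60-day limit for device shipment and device training.

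**The concern.** The plan sets out to estimate within-group means (section 13.1), with a target of 15 analysable subjects per group. For the device arm, a mean change can be interpreted only if the reader knows roughly how long subjects had the device before they were measured. The analysis names one duration, the schedule allows a range, the stated purpose names another duration, and the clock for treatment can start late.

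If Follow-up is counted from Baseline, a subject trained early and a subject trained late can both comply with the plan and yet enter the same mean after very different periods of use. The primary instruments would feel this unequally. Many RAND 36-item questions (Appendix A) look back four weeks, the PROMIS pain form (Appendix C) looks back seven days, and the symptom scale (Appendix E) asks about the present moment. For a subject trained on day 14 and seen on day 28, half of the four-week recall period came before device training, while the symptom scale would reflect only the time after it.

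**Working it through.** The plan gives no figure for time on the device at Follow-up, so there is none to reproduce. Visit timing does not enter its sample-size figure. The check is calendar arithmetic.

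**Inputs**
- Follow-up at 4-12 weeks: 4 × 7 = 28 to 12 × 7 = 84 days (Table 1).
- Completion of training, day U after Baseline: 0 to 60 (section 4.2.1, Table 1 footnote, section 6.10).
- Intended use: 3-4 weeks = 21 to 28 days (section 2.1).
- Analysis label: day 30 (section 13.2).

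Time since training is the longest that home use can have lasted. Actual use may be shorter.

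**Reading A: the window runs from Baseline (Day 0).** Time since training = F − U, with visit day F from 28 to 84. A visit earlier than day U would precede training.

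| Training day U | Earliest visit, 28 − U | Latest visit, 84 − U | Literal day 30, 30 − U |
|---|---|---|---|
| 0 | 28 | 84 | 30 |
| 7 | 21 | 77 | 23 |
| 14 | 14 | 70 | 16 |
| 30 | before training | 54 | 0 |
| 60 | before training | 24 | before training |

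A literal day-30 measurement comes before training for anyone trained on days 31-60. It gives 21-28 days since training only if U lies between 30 − 28 = 2 and 30 − 21 = 9.

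**Reading B: the window runs from training.** Time since training is 28-84 days for every subject. The visit then falls between 0 + 28 = 28 and 60 + 84 = 144 days after Baseline. The upper end, 84 days, is 84/28 = 3 times the upper end of the intended 3-4 weeks.

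**Reading C: 30 days after training.** This is 30 − 28 = 2 days beyond 3-4 weeks. It passes day 84 when U exceeds 84 − 30 = 54. For U = 60 it is day 90, 6 days over.

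**Can the passages be reconciled?** A visit 21-28 days after training that also lies within days 28-84 exists for every permitted U:
- U = 0: days 21-28, of which only day 28 qualifies.
- U = 14: days 35-42, all of which qualify.
- U = 60: days 81-88, of which days 81-84 qualify.

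So sections 2.1, 4.2.1, 5.0 and 6.10 are compatible with one another, but only under a rule that none of them states. The label in section 13.2 does not express that rule either.

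**The case against.** The strongest reply is that the label hardly matters. There is one post-baseline visit, section 4.1 points to Follow-up, and day 30 lies inside days 28-84, so the value to be analysed is not really in doubt. That stands: taken alone, the label needs only a wording correction.

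A second reply is that Table 1 places training at Baseline, with 60 days as an outer limit. A subject trained that day has 28-84 days at Follow-up on either clock. That also stands, but it does not remove the spread, and section 6.10 has the device shipped after the prescription is processed, so later training is plainly foreseen.

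A third is that the study calls itself real-world and exploratory and that the primary objective in section 3.0 names no duration. This lowers the stakes. However, the flexibility in sections 2.3.2 and 6.10 concerns the content of care and device programming, and neither section addresses when the outcome is measured. Section 13.2 permits multivariable models for imbalances but does not name timing.

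Three stronger readings are tempting, and the documents do not support them:
- *A reader might infer that exposure is undefined.* It is not. Section 2.1 gives an intended duration, and section 6.10 gives a default daily session of about 60 minutes. What is missing is the link from these to the visit.
- *A reader might infer that the arms are measured at different times after starting care.* Device shipment makes this possible, but the 60-day allowance covers prescribed care in both arms and no dates are given.
- *A reader might infer that some subjects will be measured with no device use.* The wording allows this on the Baseline clock, but section 6.10 presumes use before the next visit. The argument does not need this extreme.

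**Conclusion.** The point holds as a mismatch of timing and an unstated anchor. The 30-day wording in section 13.2 is probably a label for Follow-up. The larger matter is that training may end anywhere from day 0 to day 60 and no readable text ties Follow-up to it.

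Depending on the training day, the plan allows 28-84, 14-70 or at most 24 days since device training when counted from Baseline. Counted from training, it allows 28-84 days. Neither reading yields a 30-day or a 3-4-week change, so the device-arm mean can combine quite different lengths of use without any deviation from the plan.

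The Baseline clock is an inference from the Day 0 column heading, which is why both readings are shown. Confidence is high that the three timings do not match. It is moderate that no anchor exists, because Figure 1 is not shown and could carry one. How many subjects would be affected cannot be computed, since the documents give no training or visit dates. This should be corrected, but it does not invalidate the design.

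**What to change.** 1. Reconcile sections 2.1, 5.0 (Table 1), 6.10 and 13.2. State one time origin and one Follow-up window for both arms, such that device subjects have the intended period since completed device training before Follow-up. The sponsor sets the number.
2. Say which training date counts in the device arm, because training in conservative care and training on the device can fall on different days.
3. Replace the 30-day wording in both places in section 13.2 with the visit name used in Table 1.
4. Report days from Baseline and days since training at Follow-up, by arm (median and range), using the training-completion date.

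**Cost.** This needs protocol and SAP wording, two descriptive rows and, if the training-completion date is not already recorded, one data field. Some visits would move later. If a full 28 days since training were required, subjects trained after day 56 would pass the Day-0 window, by at most 60 + 28 − 84 = 4 days. Anchoring on training widens the spread in time since Baseline by up to 60 days, which the by-arm timing rows would show.
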